^h BPO gel should be applied for at least 5 days, in the AM immediately after the AM Cetaphil® wash. Final BPO pre-treatment should be completed at least 24 hours prior to PI application of NB01, thus final BPO application will most likely occur in the AM prior to the Day 1 (0H) visit.

ⁱ Trial subjects will note date and time of each BPO pre-treatment and Cetaphil® wash for the Screening period, and the date and time for each Cetaphil® wash during the 28-day treatment period.

^j Subjects will remain at the clinic for at least 30 minutes post application at T0H to be assessed for adverse reactions.

^k AEs will be assessed from the time of e-consent.

^l On Day 1, after baseline measurements have been obtained, subjects will then wash at the clinic before NB01 is applied by the PI.

^m Subjects initiate BID washing of their faces after waiting 24 hours from T0H, or 24H (Study Day 2). Subjects should withhold morning wash and morning facial shaving at home until they arrive at the clinic all clinic days. Once clinic day sampling has occurred, the subject may wash at the clinic. The only exception being that the subject should wash their face in the office with Cetaphil®, prior to the Day 2 Bioré® Strip follicular engraftment sampling

ⁿ Study procedures are completed as needed, as clinically indicated, for unscheduled study visits.

^o The EOS Visit should be completed on Day 28, or prior to the initiation of new anti-acne therapy. Should the subject discontinue the study early, the EOS should be scheduled and completed as soon as possible.

^p No other cleansers can be used throughout the study, from the Screening Visit to Day 28/EOS.

^q Subjects will hold the PM Cetaphil® wash prior to the Day 1 study drug application.

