4 STUDY DESIGN

4.1 OVERALL DESIGN

This is a first human, single-center, dose escalation, open-label trial of a single application of topically delivered NB01 in subjects with moderate, non-cyclical facial acne.

Ten subjects will be assigned to 1 of 2 dose cohorts in a stepwise fashion after a 5-day pre-treatment with 5.0% daily BPO gel (<https://www.perrigo.com/business/product.aspx?ID=88&let=B> Perrigo 5% BP Aqueous Gel).

- Cohort 1: 10⁵ CFU/cm² NB01
- Cohort 2: 10⁶ CFU/cm² NB01

This will be ascending dose finding whereby 5 initial subjects will be assigned to Cohort 1 to receive a single application of 10^5 CFU/cm² to the facial skin of the nose/cheek. If there are less than 2 dose-limiting toxicities (DLTs) during the 7-day safety assessment, a Dose Escalation Meeting will be held between the PI and the Sponsor Medical Monitor to determine whether Cohort 2 will be opened to enrollment.

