5.5 ENROLLMENT PROCEDURES AND TREATMENT ASSIGNMENT

The screening date will be defined as the date the subject signs the ICF. Subjects will be screened within 5 days (+2 days) of enrollment to determine eligibility for participation in the study. Screening laboratory results for hematology (Complete Blood Counts [CBC]) should be obtained from the local laboratory. Screening procedures (Section 8.1) will be performed and documented, at the end of which the clinical site will complete subject and visit information on the Enrollment Request Form (ERF) for Sponsor approval. Approved subjects who meet all inclusion criteria and none of the exclusion criteria may be enrolled into the trial.

It is the responsibility of the PI to ensure that subjects are eligible for the study prior to enrolling into the study. Subjects who do not enroll within the Screening Period will be screen failed. A subject will be considered enrolled once he or she has signed the ICF, met all inclusion/exclusion criteria, executed all screening visit measurements, including daily BPO therapy, and received Sponsor approval to participate.

This is an open-label study. Subjects will be assigned a unique Screening Number at the time of e-consent. Subjects who have met all eligibility criteria will initiate an at-home daily application of a 5.0% BPO gel treatment, and BID Cetaphil® wash and complete an electronic, in-home patient diary (e-diary). They will return to the clinic on Day 1 to perform baseline assessments. Day 1 is defined as the date the first application of NB01 will occur. All baseline tests and procedures must be completed prior to the application of the first dose of study drug on Day 1, time point 0H. Once eligibility is confirmed, subjects will be assigned a unique Subject ID number and be assigned to a cohort. Once a Subject ID has been assigned to a subject, it will not be reassigned to another subject.

Each on-study visit will be scheduled relative to Day 1 0H. Enrolled subjects will complete an in-home e-diary to capture at home Cetaphil® washing through the end of the study. Visits will follow the SOE table and protocol section 8.1. The ERF and additional details can be located in the Study Reference Manual for the trial.

Re-Screening of Subjects

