Subjects who screen fail may be considered for enrollment at a later date, but must re-sign the ICF and repeat screening procedures, if any screening procedures will be performed outside of the Screening period from the time of the first informed e-consent.

Replacement of Subjects

If a subject is discontinued from the study for any reason other than a dose-limiting toxicity (DLT) prior to completion of the DLT assessment window, a replacement subject will be enrolled at the same dose level as the discontinued subject. To be evaluable for the DLT observation, a subject must receive a dose of NB01 and either completes all safety procedures through Day 7 or experiences a DLT prior to Day 7. It is possible over-enrollment of subjects may occur in order to have 10 safety-evaluable subjects.

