8 STUDY ASSESSMENTS AND PROCEDURES

8.1 SAFETY AND OTHER ASSESSMENTS

Subjects will come to the clinic for the following protocol-specified visits: Screening, 0H (+2-day window), 6H, 24H, 48H, 7 days (± 1 -day window) and 28 days (± 3 -day window) days post application. It is important that the 6H, 24H and 48H visits be on approximately on time (± 2 -hour window) to ensure engraftment can be properly assessed.

Screening

Once the subject has provided consent to participate, the following required procedures will be completed at the Screening Visit:

- Review of subject eligibility based on inclusion and exclusion criteria
- Vitals: Blood pressure, heart rate and temperature
- Labs:
 - CBC
 - Urine dipstick pregnancy test (females of childbearing potential)
- Screening IGA score and total lesion count
- Screening porphyrin and sebum levels (Pear 3D)
- Screening photographs (Pear 3D)
- Screening pH (pH meter)
- A pre-BPO cheek swab sample will be procured
- Pre- Bioré® sampling facial wash with Cetaphil®
- A pre-BPO Bioré® sample will be obtained

The following procedures will be completed within the Screening Period:

- Subjects will initiate 5-day, at-home pre-treatment with a 5.0% BPO gel daily application to the face (<https://www.perrigo.com/business/product.aspx?ID=88&let=B> Perrigo 5% BP Aqueous Gel) at the same time each day, immediately after the AM Cetaphil® wash. The final BPO gel application should be at least 24 hours prior to study drug application (and therefore likely the morning before the Day 1 (0H) visit)
- Subjects will initiate a 5-day at-home BID Cetaphil® wash at the same time each day, with the PM wash to be held the day before the Day 1 (0H) visit. No other cleansers can be used throughout the study, from the Screening Visit to Day 28/EOS.
- Subjects will complete an in-home patient e-diary during the pre-treatment period

Once the subject's eligibility has been confirmed and pre-treatment BPO period completed, the subject will be enrolled into the study and initiate on-study procedures, including ongoing patient e-diary for Cetaphil® washes.

Treatment Period

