The following will be completed at all office study visits (0H, 6H, 24H, 48H, 7 days, and 28 days), unless otherwise specified:

- Assess for any new or existing AEs or SAEs
- Review concomitant medications
- Obtain cheek samples for
 - Porphyrin presence (Pear 3D)
 - Sebum production (Pear 3D)
- Photography (Pear 3D)
- IGA
- Absolute lesion counts
- pH of skin (pH meter)
- Assess engraftment via Fab-Swab Filtered Air Breathable Sterile Flocked Collection Device (PurFlock® Ultra-Puritan Diagnostics) (TaqMan® assay)
- Assess follicular engraftment via Bioré® strip (TaqMan® assay, at 24H only)
- Urine dipstick pregnancy test (females of childbearing potential, at 0H and Day 28 only)

NOTE: Additional vital signs and CBC may be repeated, as clinically indicated.

End of Study (EOS)

Subjects will remain in the study through Day 28, or may discontinue early, as described in protocol section [7.1](#). Subjects will have completed the study upon conclusion of the Day 28/EOS visit procedures. Subjects who discontinue prior to Day 28 should have the EOS visit scheduled as soon as possible, in

order to complete final safety assessments, prior to discontinuation from the study.

Early Discontinuation of Subjects

Subjects may voluntarily withdraw from the study at any time. A subject's participation in the study may be terminated if it is deemed by the PI or Sponsor that it is unsafe for the subject to continue in the study. Subjects who discontinue prior to completing the DLT evaluation period (i.e., prior to completion of Day 7 procedures) for reasons other than a DLT, will be replaced.

Notification of early subject discontinuation from the study and the reason for discontinuation will be made to Sponsor and will be clearly documented on the appropriate eCRF.

Study Termination

The study may be stopped at his/her study site at any time by the site PI. Sponsor may stop the study (and/or the study site) for any reason with appropriate notification. Both the Sponsor and the PI reserve the right to terminate the study at any time. Should this be necessary, both parties will arrange discontinuation procedures and notify the appropriate regulatory authority(ies), and IRBs. In terminating the study, Naked Biome and the PI will assure that adequate consideration is given to the protection of the subjects' interests.

Adverse Events (AEs)

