8.2.2 DEFINITION OF DOSE-LIMITING TOXICITIES (DLTs)

Dose-limiting toxicities (DLTs) are defined as AEs occurring during the first 7 days after NB01 application that are not due to the subject's underlying disease, are not clearly attributable to other etiologies, and meet any of the following toxicity criteria:

Dermatologic Toxicities:

- Skin Dryness Score of 3
- Skin Peeling Score of 3
- Irritant/Allergic Contact Score of 3
- Hyperpigmentation Score of 3
- Skin Erythema Score of 3
- Exacerbation of disease determined by an increase in IGA score 1 point beyond baseline screening score

Ocular Toxicities:

- Conjunctival injection score of 3
- Eye irritation score of 3

Mucosal Toxicities:

- Mucosal Irritation Score of 3

If any systemic toxicities develop, the Sponsor will pause the study for further review before proceeding. If 2 or more subjects experience a DLT, or in the event of an SAE that is at least possibly-related to study treatment, the Sponsor will pause the study to discuss with the PI and regulatory authorities, if needed.

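### DLTs are defined over 7 days, but the visit that closes DLT evaluation may fall at 6 days, so a new onset in the last 24 h can go without scheduled review before Cohort 2 opens

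*Combined protocol and SAP*

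**What the plan says.** Section 8.2.2 defines DLTs as "AEs occurring during the first 7 days after NB01 application" that meet listed criteria. Each criterion is a clinician rating: a tolerability score of 3, or a one-point rise in IGA over the screening score.

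Section 4.1 sets the condition for the dose step: "If there are less than 2 dose-limiting toxicities (DLTs) during the 7-day safety assessment", the PI and the Medical Monitor meet to decide whether Cohort 2 opens. Section 8.1 adds that there must be no possibly related SAE in Cohort 1.

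Timing runs from application. Section 5.5 states: "Each on-study visit will be scheduled relative to Day 1 0H". Section 8.1 lists the last two visits as "7 days (± 1 -day window) and 28 days (± 3 -day window) days post application", and the Schedule of Events gives the same windows.

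Three rules depend on the 7-day visit:
- **Evaluability (5.5):** a dosed subject counts if he or she "either completes all safety procedures through Day 7 or experiences a DLT prior to Day 7".
- **End of the DLT period (8.1):** subjects are replaced if they leave for a reason other than a DLT "prior to completing the DLT evaluation period (i.e., prior to completion of Day 7 procedures").
- **Escalation call (11.1.6):** it is convened once the first five safety-evaluable Cohort 1 subjects have finished their Day 7 assessments.

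None of the three sets a minimum elapsed time.

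**The concern.** The definition of a DLT and the rule that ends the search for one use different clocks. The definition runs to 168 h, whereas the closing rule runs to a visit that can be on schedule at 144 h. A site that follows the protocol exactly can count a subject as fully evaluated, and hold the call, while part of that subject's DLT window has not been reviewed.

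The call governs the only dose step in the trial: from 10^5 to 10^6 CFU/cm², with a live organism for which Section 2.2 reports no in vivo data. Section 4.1 presents that step as resting on a 7-day safety assessment. For a subject seen early, the rules guarantee six days.

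**Working it through.** **Inputs.** DLT window: 7 days (8.2.2). Closing visit: 7 days ±1 day after application (Schedule of Events, 8.1). Next scheduled visit: 28 ±3 days. Gate: fewer than 2 DLTs, with five evaluable subjects (4.1, 10.3). Section 10.2 gives no sample size or power calculation, and the documents state no DLT rate or onset pattern, so there is no planned figure to reproduce.

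**Step 1: the gap.** Window: 7 × 24 = 168 h. Earliest on-schedule closing visit: 168 − 24 = 144 h. Gap: 168 − 144 = 24 h, and 24/168 = 14.3% of the window. Visits at 168 to 192 h leave no gap. This step needs no assumption about toxicity.

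**Step 2: when the gap is next reviewed.** The next scheduled scoring is at 28 ±3 days, that is 25 to 31 days (from 25 × 24 = 600 h). Before then, Section 8.2.1 offers two routes: the subject volunteers the event between visits, or an AE already detected is being followed, more often than at visits if necessary. Either can lead to scoring at an unscheduled visit. A new, unreported onset between 144 and 168 h reaches neither.

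**Step 3: is BPO pre-treatment a buffer?** The Schedule of Events, footnote h, says "BPO gel should be applied for at least 5 days". If Cohort 2 screening started only after a call at 144 h, the first high dose would come no earlier than 144 + 5 × 24 = 264 h, past 168 h. But the call opens enrollment, and under Section 5.5 a subject is enrolled only after having "executed all screening visit measurements, including daily BPO therapy, and received Sponsor approval to participate". Screening and BPO could therefore run before the call. Even with the delay, nothing schedules a score for the missing day before 600 h.

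**Step 4: illustration of size.** Assumptions, none taken from the documents: 7-day DLT rate *p* of 10%, 20% or 1/3; onset uniform over 7 days; at most one DLT per subject; the gate opens automatically at 0 or 1 DLT in 5; no late DLT is found before the call. A subject seen at 144 h has an observed rate of *p* × 6/7. With visits spread evenly over 6 to 8 days, the mean unobserved time is 0.25 day (half the visits are early, by 0.5 day on average), so the rate is *p* × (1 − 0.25/7). With a common rate *q*, P(gate opens) = (1 − q)^5 + 5q(1 − q)^4.

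Example, *p* = 0.20, full window: 0.3277 + 0.4096 = 0.7373. All five at 144 h: q = 0.20 × 6/7 = 0.1714, giving 0.3905 + 0.4040 = 0.7945, a rise of 5.7 points.

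| Assumed rate | Full window | One subject at 144 h | Five spread over 144–192 h | All five at 144 h |
|---|---|---|---|---|
| 10% | 91.9% | 92.3% (+0.4) | 92.4% (+0.5) | 93.8% (+2.0) |
| 20% | 73.7% | 74.9% (+1.2) | 75.2% (+1.5) | 79.5% (+5.7) |
| 1/3 | 46.1% | 48.0% (+1.9) | 48.5% (+2.4) | 55.8% (+9.7) |

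If half of the late DLTs are found and scored before the call, the rises are 0.2, 0.6 and 0.9 points (one early), 0.3, 0.7 and 1.2 (spread), and 1.0, 2.9 and 4.8 (all early). If all are found, the rise is zero.

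**The case against.** The best defence is that the protocol has one consistent operating rule: evaluability, the end of the DLT period and the call all close on the Day 7 procedures, and ±1 day is an ordinary visit tolerance. Other safeguards also apply. The decision belongs to the PI and Medical Monitor and is not automatic; Section 8.1 also bars escalation after a possibly related SAE; Section 10.3 places the high dose after AE evaluation of the low-dose subjects; the pause at two or more DLTs in Section 8.2.2 is not limited to the time before the call. Subjects dosed earlier may be well past 168 h when the call is held. All of this limits the effect. But these safeguards act on events that have come to light, and none schedules a review of the last day.

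The objection to the percentages also stands in large part. Uniform onset has no support in the documents; if reactions cluster soon after application, the figures shrink. The gate is modelled as automatic, and everything before the visit as captured, although there is no scheduled scoring between 48H and the 7-day visit.

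A reader might infer two stronger claims:
- **A gap of 48 h.** Counting the Day 7 label from Day 1 = application puts the nominal visit at 144 h and the earliest at 120 h. The documents do not support this: the Schedule of Events header gives 7 days, Section 8.1 says post application, and Section 5.5 times visits from 0H. The label is an inconsistency and nothing more.
- **A late DLT is seen only if the subject volunteers it.** Section 8.2.1 also requires follow-up of detected AEs, so a reaction visible at 144 h that later worsens to a score of 3 should be picked up. The exposure is to new onsets.

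**Conclusion.** The point holds and is minor. As written, Cohort 2 may open with up to 24 h of the 168 h DLT window (14%) lacking scheduled review for any Cohort 1 subject seen early. That follows from the text alone. It does not follow that a DLT would be missed, or that the chance of opening the gate rises by any particular amount. The percentages are illustrations under assumed rates, uniform onset and an automatic gate. The 9.7-point figure is an extreme that needs all five visits at exactly 144 h, a rate of one in three and no late event found. The reason to act is that the correction is cheap and concerns the only escalation decision.

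**What to change.** In Sections 5.5, 8.1 and 11.1.6, require that each of the five evaluable Cohort 1 subjects has reached 168 h and had a safety assessment at or after 168 h, or has had an earlier DLT, before the escalation call. The simplest way is to change the 7-day visit window to 7 days +1 day and, at that visit, ask about events since the last visit and their onset dates. The Schedule of Events already uses a plus-only window for the 0H visit. The Day 7 label can be aligned at the same time.

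This adds no planned visit and leaves 0 h of the window unreviewed. Its costs:
- The earliest call is up to one day later; the latest permitted visit stays at 192 h.
- The visit window narrows from 48 h (144–192 h) to 24 h (168–192 h), with possibly more deviations. A subject seen too early would need a repeat assessment or replacement.
- Ignoring the ±2 h tolerance at 48H, the minimum unscored stretch after that visit rises from 144 − 48 = 96 h to 168 − 48 = 120 h, so a short-lived reaction is somewhat less likely to be scored while present. The maximum, 192 − 48 = 144 h, is unchanged.
- For visits after 168 h, whether a score of 3 began inside the window depends on the reported onset.

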7 STUDY INTERVENTION DISCONTINUATION AND PARTICIPANT DISCONTINUATION/WITHDRAWAL

7.1 PARTICIPANT DISCONTINUATION/WITHDRAWAL FROM THE STUDY

Participants are free to withdraw from participation in the study at any time.

Participants will remain in the study through Day 28, or may discontinue early if any of the following criteria are met:

- PI decision
- Subject withdrawal of consent
- Subject is lost to follow-up
- Unacceptable Toxicity (exacerbation of IGA 1 point higher than baseline)
- Sponsor termination of the trial

A PI may discontinue a participant from the study for the following reasons:

- Pregnancy
- Failure to comply with the study procedures, including inability to receive study drug or missing study appointments
- If any clinical AE, laboratory abnormality, or other medical condition or situation occurs such that continued participation in the study would not be in the best interest of the participant
- Disease progression, which requires discontinuation of the study intervention

The reason for participant discontinuation from the study will be recorded on the Case Report Form (CRF)/electronic CRF (eCRF).

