The PI must also complete the Serious Adverse Event Report Form, in English, notify the Sponsor and, if necessary, send the completed and signed form to the Sponsor or designee within 24 hours of becoming aware of the SAE. The PI must provide a causality assessment, that is, assess whether there is at least a reasonable possibility that the SAE is related to the study treatment: suspected (yes) or not suspected (no).

Investigational site personnel must report any new information regarding the SAE within 24 hours of becoming aware of the information in the same manner that the initial SAE Report Form was sent. Follow-up information is recorded on an amended or new SAE Report Form, with an indication that it is follow-up to the previously reported SAE and the date of the original report. The follow-up report should include information that was not provided on the previous SAE Report Form, such as the outcome of the event (e.g., resolved or ongoing), treatment provided, action taken with study drug because of the SAE (e.g., dose reduced, interrupted, or discontinued), or subject disposition (e.g., continued or withdrew from study participation). Each recurrence, complication, or progression of the original event should be reported as follow-up to that event, regardless of when it occurs.

The treating PI will determine AEs by:

- Active query for any systemic symptoms
- Limited facial physical examination
- Utilization of Investigator Assessment of Tolerability Scale (0 = None; 1 = Slight; 2 = Moderate; 3 = Intense) for assessment of:
 - Skin Dryness
 - Skin Peeling
 - Irritant/Allergic Contact Dermatitis
 - Hyperpigmentation
 - Skin Erythema
 - Conjunctival Injection
 - Ocular Irritation
 - Mucosal Toxicity
- Assessment of disease status using IGA Score and Acne Lesion Count

Toxicities that warrant subject discontinuation from the trial, as deemed appropriate by the PI, include but are not limited to: ulceration, extreme redness, worsening of acne, extreme skin irritation, extreme ocular irritation, extreme mucosal irritation, extreme contact dermatitis.

REPORTING

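### The DLT list omits ulceration, so a subject withdrawn for it before completing Day 7 is replaced and goes uncounted; the underlying-disease exclusion can also void the listed IGA item

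*Combined protocol and SAP*

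**What the plan says.** **DLT definition (8.2.2).** A DLT is an AE in the 7 days after application that is not due to the subject's "underlying disease, are not clearly attributable to other etiologies, and meet any of the following toxicity criteria". Nine criteria follow: a score of 3 on each of eight tolerability items, and a one-point rise in IGA over screening. There is no catch-all, severity-grade or withdrawal item.

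**Toxicity withdrawal (7.1, 8.1, 8.2.1).** These provisions are wider.
- Section 8.2.1 says the toxicities warranting discontinuation "include but are not limited to: ulceration, extreme redness, worsening of acne, extreme skin irritation" and several further extreme reactions.
- Section 7.1 lets the PI withdraw a subject if "any clinical AE, laboratory abnormality, or other medical condition or situation occurs such that continued participation in the study would not be" in the participant's best interest.
- Section 8.1 says participation "may be terminated if it is deemed by the PI or Sponsor that it is unsafe for the subject to continue in the study".
- Section 7.1 also lists as a ground for early discontinuation "Unacceptable Toxicity (exacerbation of IGA 1 point higher than baseline".

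**Evaluability and replacement (5.5, 8.1).** For a subject "discontinued from the study for any reason other than a dose-limiting toxicity (DLT) prior to completion of the DLT assessment window, a replacement subject" is enrolled at the same dose level. To be DLT-evaluable, a subject must be dosed and "either completes all safety procedures through Day 7 or experiences a DLT prior to Day 7". Section 8.1 repeats that subjects who leave "prior to completion of Day 7 procedures) for reasons other than a DLT, will be replaced".

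**Escalation.** Section 6.1.1 words Cohort 2 dosing as following from fewer than 2 DLTs in Cohort 1, and 8.1 adds the absence of a possibly related SAE. Sections 4.1 and 11.1.6 place a decision by the PI and the Medical Monitor in between, taken once the first 5 evaluable subjects have finished Day 7. Under 8.2.2 the study pauses for 2 or more subjects with a DLT, for an SAE at least possibly related, or for any systemic toxicity.

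**The concern.** The discontinuation list is open and the DLT list is closed, and replacement depends on the closed one. Ulceration falls between them: it warrants withdrawal, but it is neither a DLT criterion nor an item on the Appendix C scale. A subject withdrawn for it before completing Day 7 drops out of both the numerator and the five evaluable subjects on which escalation is judged. The same holds for any other local, non-serious NB01 toxicity that reaches no listed criterion.

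The second problem is internal to 8.2.2. The underlying disease is acne, and the lead-in removes events due to it. The list then includes exacerbation of that disease. Every subject enters at IGA grade 3 (5.1), so a one-point rise is grade 4, severe acne. An investigator who attributes the flare to acne can take it out of the count, although 7.1 treats the same change as a toxicity.

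This is a first-in-human study with a tenfold dose step (10^5 to 10^6 CFU/cm²), and the DLT count is its main numerical safeguard. That count should include an NB01-related toxicity bad enough for the PI to remove the subject.

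**Working it through.** The plan states no DLT rate, power or error figure (10.2), so there is nothing to reproduce. The text alone settles whether the gap exists. Its size needs assumed rates.

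**Step 1. Map the toxicities named in 8.2.1 to DLT criteria.**

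| Named in 8.2.1 | Criterion in 8.2.2 |
|---|---|
| Extreme redness | Erythema score 3 |
| Extreme skin irritation or contact dermatitis | Irritant/allergic contact score 3 |
| Extreme ocular irritation | Eye irritation or conjunctival injection score 3 |
| Extreme mucosal irritation | Mucosal irritation score 3 |
| Worsening of acne | IGA +1, subject to the exclusion |
| Ulceration | None |

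**Step 2. Follow the rules with no assumed rates.**
- One listed DLT and one ulceration withdrawal among the first 5 dosed, with an uneventful replacement: 1 of 5 as written, 2 of 5 if the withdrawal counts.
- Two ulceration withdrawals, no listed DLT and uneventful replacements: 5 + 2 = 7 dosed, 0 of 5 as written, 2 of 5 if they count.

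In each case the criterion is met as written and failed if the exits count.

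**Step 3. Size under assumed rates.** Let a be the listed-DLT rate and c the rate of unlisted toxicity withdrawals before Day 7 is complete, both per dosed subject. The criterion is met with probability P(X ≤ 1) = (1−p)^5 + 5p(1−p)^4, where p is:
- as written (exits replaced): p = a/(1−c)
- exits kept in the denominator but uncounted: p = a
- exits counted: p = a + c

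Example, a = 0.10 and c = 0.02. As written, p = 0.10/0.98 = 0.102, giving 0.916. Counted, p = 0.12, giving 0.888. The gap is 0.028.

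| a | c | As written | Uncounted, not replaced | Counted |
|---|---|---|---|---|
| 0.10 | 0.01 | 0.917 | 0.919 | 0.903 |
| 0.10 | 0.02 | 0.916 | 0.919 | 0.888 |
| 0.10 | 0.05 | 0.911 | 0.919 | 0.835 |
| 0.10 | 0.10 | 0.902 | 0.919 | 0.737 |
| 0.05 | 0.02 | 0.977 | 0.977 | 0.958 |
| 0.20 | 0.02 | 0.729 | 0.737 | 0.696 |

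At a = 0.10 the gap between as written and counted is 0.014, 0.028, 0.076 and 0.164 as c rises from 0.01 to 0.10. The third and fourth columns show that replacement by itself does not loosen the count (0.902 against 0.919 at 10% and 10%). The loosening comes from the closed list.

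These are probabilities of meeting the numerical criterion, not of opening Cohort 2. Ulceration in subjects who stay to Day 7, which also goes uncounted as written, is not modelled.

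**Step 4. IGA clause.** Assume 5% score-3 events and 5% IGA +1 events.
- Voided, subject stays: p = 0.05, giving 0.977.
- Voided, subject withdrawn and replaced: p = 0.05/0.95 = 0.0526, giving 0.975.
- Counted: p = 0.10, giving 0.919.

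**The case against.** The strongest reply is that very little gets through. Step 1 leaves ulceration as the only named toxicity without a criterion, and an investigator might score it as intense irritant dermatitis. It could also be judged a medically important SAE, which blocks Cohort 2 under 8.1 if possibly related. Early withdrawal is itself unlikely: there is a single application, so leaving the study stops no further dosing. The PI who withdrew the subject also takes part in the escalation decision. On the IGA item, a specific listed criterion is not naturally read as cancelled by its own lead-in, 7.1 shows the intent, and 8.3 treats the study product as always suspect.

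Most of this stands, and it limits the point to a small class of local, non-serious events. It does not close the gap. Nothing directs that ulceration be scored as dermatitis or reported as an SAE, and no rule says how a replaced toxicity exit is to be weighed at the meeting. For the IGA item, 8.2.1 requires worsening events to be marked as related or not to disease progression, but does not say which mark makes the event a DLT. With no control arm or blinding, a natural flare cannot be reliably told from one caused by NB01.

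A reader might infer that toxicity withdrawals in general escape the count, or that Cohort 2 opens automatically once fewer than 2 DLTs are counted. The documents support neither. Any reaction scoring 3 counts even if the subject leaves, and 4.1 and 11.1.6 require a decision. Nor are the events lost, because all AEs are recorded whatever the subject's evaluability.

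**Conclusion.** The point holds in a narrow form. Applied as written, 8.2.2 with 5.5 and 8.1 leaves a subject withdrawn for ulceration, or for another unlisted, local, non-serious NB01 toxicity, out of the DLT count and out of the five evaluable subjects. That conclusion rests on the text alone. The size rests on assumed rates: it is small at 1–2% exits (0.014–0.028 at a 10% listed-DLT rate) and reaches 0.164 only if exits are as common as 10%, for which the documents give no basis.

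The conflict over the IGA item is also real on a literal reading, and it is worth 0.977 against 0.919 under the 5% and 5% assumption. It would go too far to say that IGA +1 never counts: 7.1 points the other way, and the defect is that the text allows both readings. Both are wording faults in a first-in-human stopping rule and are worth correcting before Cohort 1 is dosed.

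**What to change.** 1. In 8.2.2 add two DLT criteria: (i) ulceration at the application site; (ii) any other AE of at least moderate severity, at least possibly related to NB01, for which the PI or Sponsor withdraws the subject before Day 7 is complete. In 5.5 and 8.1 state that these subjects are DLT-evaluable and are not replaced. Acne worsening stays governed by the IGA item alone. The severity floor matters because, under one of the two causality scales in 8.3, timing alone can make an event possibly related.

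2. In 8.2.2 state that a one-point IGA rise over screening within 7 days is a DLT despite the underlying-disease exclusion, unless a definitive alternative etiology other than acne itself is documented.

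The cost is a few sentences in three sections, with no added visits or subjects. The downside is that a toxicity withdrawal, or an acne flare after BPO stops, may delay Cohort 2. One limit remains: criterion (ii) depends on a discretionary withdrawal, so the same event in a subject who stays would not count. Ulceration would count either way.
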